Assessment appointment. In addition, at weeks 1, 3 and 5, the Veteran will complete the primary and secondary functioning outcome measures (WHOQOL-BREF and FOSQ-10.) \*Completion of ISI and ESS, sleep diary data, and PAP adherence are part of routine care and will also be used for research purposes. The additional WHOQOL-BREF AND FOSQ-10 at weeks 1, 3 and 5 are for research purposes.

**Post-Treatment Assessment.** One week following his or her final treatment appointment, the Veteran will attend the post-treatment assessment appointment via phone or video. He or she will turn in the sleep diary with data from the preceding week. He or she will turn in the actigraphy device. The Veteran will complete post-treatment questionnaires. A trained, blinded clinical interviewer will repeat the CAPS-5 interview (current symptoms only) and SCID-5 (insomnia portion only) and inquire about medication changes. The Veteran will complete a brief feedback interview about their treatment experience with study staff. The Veteran's PAP adherence data will be downloaded or provided verbally. \*This is for research purposes.

**3-Month Follow-Up Assessment.** Veterans will complete the 3-month follow-up questionnaires. PAP adherence data will be downloaded or provided verbally. If the Veteran's PAP device does not have a functional modem, the study team will arrange for the Veteran to provide their SD card for data download. The data will be uploaded to the appropriate clinical data monitoring system and the SD card will be returned to the Veteran. Veterans' charts will be checked to track PAP follow-up appointment attendance, if applicable. Veterans will be sent a sleep diary to complete the week prior to this appointment and will submit it at this appointment. \*This is for research purposes. However, review of PAP adherence data at 3-month follow-up is also part of routine care in the Sleep Clinic.

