**PAP desensitization.** PAP desensitization is a type of graded exposure that is used to acclimate Veterans to PAP. This is indicated in the case of Veterans who have increased difficulty falling asleep or back asleep with the mask on, experience anxiety or claustrophobia when using PAP, or who those who remove PAP (either consciously or unconsciously) while asleep. The Veteran will use their PAP (with mask and machine on) while awake. He or she will engage in another activity, such as listening to music or watching TV, rather than focusing on his or her breathing. By acclimating to the sensation of the PAP device while awake, the Veteran will become more comfortable using the device at night and will be more likely to tolerate it overnight. The therapist first explains the rationale for PAP desensitization to the Veteran. For Veterans with anxiety or claustrophobia caused by PAP, the therapist will introduce the Veterans to a rating scale to indicate their level of discomfort so that reductions in anxiety can be tracked. The therapist will also discuss coping strategies the Veteran can use while engaging in desensitization. The therapist will guide the Veteran through an in-session desensitization practice. Should the Veteran experience anxiety, the therapist will coach the Veteran through using coping skills and observing his or her anxiety levels decrease over the course of exposure. The therapist will then work with the Veteran to generate a plan for engaging in desensitization at home. It is recommended that the Veteran complete desensitization for 30 minutes daily.

**Cognitive Behavioral Therapy for Insomnia (CBT-I).** CBT-I is an established behavioral treatment for insomnia. Its main components are sleep restriction therapy and stimulus

control. Secondary components include sleep hygiene, cognitive strategies, and relaxation techniques.

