### Apnea and Insomnia Relief (AIR) session content

Session	Content
1	Psychoeducation about sleep apnea, insomnia, and PTSD; assessing/increasing motivation and identifying goals for treatment; learning to complete sleep diary
2	Continued motivational interviewing; Reviewing PAP experience; introducing PAP desensitization (in-session and at home) if needed; reviewing sleep diary; learning about sleep restriction
3	Reviewing PAP experience; continuing PAP desensitization; reviewing sleep diary; introducing stimulus control; continued motivational interviewing, if needed
4	Reviewing PAP experience; continuing PAP desensitization; reviewing sleep diary; sleep hygiene; continued motivational interviewing, if needed
5	Reviewing PAP experience; continuing PAP desensitization; reviewing sleep diary; cognitions about sleep; relaxation strategies; continued motivational interviewing, if needed
6	Reviewing PAP experience, continuing PAP desensitization; reviewing sleep diary; reviewing progress and relapse prevention

**Sleep Education Control (SE).** The control treatment will also be offered over 6 sessions via telehealth, to match time with the attention provided in the AIR condition. The protocol is an adaptation of the non-directive sleep education control condition in a study of CBT for insomnia among older adults at the Greater Los Angeles Healthcare System. Topics covered include the sleep cycle, sleep across the lifespan, sleep and the mind, evening activities and the sleep environment, and daytime activities and sleep. The table beneath this description provides for a session-by-session overview of the treatment.

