Analyses for PAP adherence: PAP adherence will be measured via device data capture. The primary metric used to measure this will be average hours of PAP use in the past 7 days. This will be measured starting at session 1 and will continue through post-treatment, and again for 1 week at follow-up. A linear mixed model as described above for the ISI will be estimated for PAP adherence. The hypothesis will be tested by the significance of the group difference in marginal means at post-treatment derived from the full model. The difference in marginal means at post-treatment will be divided by the pre-treatment standard deviation to calculate the standardized effect size. Durability of effects at 3 months will be tested by comparing model-adjusted marginal effects for the two groups at follow-up. Effect size of treatment at 3 months will be calculated from the marginal effect of group at follow-up divided by the standard deviation of week 1 adherence scores. Hypothesis 2a: Veterans receiving the behavioral sleep treatment will report at least moderate agreement with items on the Feasibility and Acceptability Questionnaire. Analyses: Descriptive statistics will be calculated for each item of the Feasibility and Acceptability questionnaire, provided in the Appendix. The mean response to each item will be the primary metric for evaluation of this hypothesis. A mean in the range of 4.0 to

**Hypothesis 2b:** There will be lower dropout in the AIR condition compared with the SE condition.

**Analyses:** We will conduct a chi-square analysis to compare dropout in the two conditions (completed all six sessions vs. not).

**Hypothesis 2c:** There will be greater engagement in apnea care in the AIR condition compared with the SE condition.

**Analyses:** We will conduct a chi-square analysis to compare how many Veterans attend their first PAP follow-up appointment with a sleep technician or sleep NP in the two conditions.

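### Awake PAP desensitization practice, given only in AIR and only when indicated, can count as adherence in the post-treatment PAP comparison

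*Combined protocol and SAP*

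**What the plan says.** Under Hypothesis Testing (Hypothesis 1b, analyses for PAP adherence) the source is given as "PAP adherence will be measured via device data capture" and the metric as "The primary metric used to measure this will be average hours of PAP use in the past 7 days". The test is the group difference in marginal means at post-treatment, with a durability comparison at 3 months. Nothing there limits the hours to sleep, night or time in bed.

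Under Intervention Descriptions, the paragraph on PAP desensitization says: "The Veteran will use their PAP (with mask and machine on) while awake". On the amount of home practice it says: "It is recommended that the Veteran complete desensitization for 30 minutes daily". It is not meant for everyone: "This is indicated in the case of Veterans who have increased difficulty falling asleep or back asleep with the mask on". Anxiety or claustrophobia with PAP, and removal of the device during sleep, are further indications.

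The AIR session content table brings it in at session 2 as "introducing PAP desensitization (in-session and at home) if needed" and still lists it at session 6: "Reviewing PAP experience, continuing PAP desensitization; reviewing sleep diary; reviewing progress and relapse prevention". The Sleep Education Control session table contains no PAP practice.

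Under Data Collection Procedures, the post-treatment assessment takes place one week after the last session, and device download is not the only source: "The Veteran's PAP adherence data will be downloaded or provided verbally".

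**The concern.** The PAP hypothesis is about treating apnea, which happens while the Veteran sleeps. Awake practice is a step towards that, not an instance of it. If the device logs practice as use, part of one arm's treatment is scored as that arm's outcome, in the hypothesized direction. A reported gain in hours could then not be separated from homework. That matters because this pilot is meant to shape a full-scale trial.

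The exploratory analyses are also exposed. The adherence bands cut at 1 and 4 hours a night, and practice can move a Veteran across a cut: 0.6 + 0.5 = 1.1 h, or 3.6 + 0.5 = 4.1 h. The analysis of CBT-I in Veterans not adherent to PAP could lose some AIR Veterans for the same reason, so that the subset is selected differently in the two arms.

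**Working it through.** The documents give no SD, effect size, alpha or power for PAP hours, so there is no stated figure to reproduce. The check asks how large the artefact can be.

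**From the documents**
- Recommended practice: 30 minutes daily = 0.5 h/day, or 0.5 × 7 = 3.5 h in the scored week.
- Arm: AIR only, among Veterans with an indication.
- Timing: listed through session 6; the 7-day window at post-treatment directly follows that session.
- Sample size: 40 per arm (Objective, Aim 1).

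**Assumed**
- Share of the AIR arm still practising in the scored week: 25–75%.
- Compliance with the recommended minutes: 50–100%.
- Between-person SD of 7-day mean hours: 2.0–2.5 h.
- Two-sided 5% test, complete data, no true difference in other use, no practice in the control arm. A simple two-sample normal approximation stands in for the mixed model.

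**Formulas**
- Artefact b = 0.5 × share × compliance.
- Standardized size = b / SD.
- Standard error = SD × √(2/40): 0.447 h for SD 2.0 and 0.559 h for SD 2.5.
- Shift z = b / standard error.
- Rejection rate = 1 − Φ(1.96 − z) + Φ(−1.96 − z).

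**Results**

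| Share × compliance | b (h/day) | b/SD, SD 2.5 to 2.0 | Rejection, SD 2.5 to 2.0 |
|---|---|---|---|
| 25% × 50% | 0.06 | 0.03 to 0.03 | 5.1% to 5.2% |
| 50% × 75% (mid-range) | 0.19 | 0.08 to 0.09 | 6.3% to 7.0% |
| 50% × 100% | 0.25 | 0.10 to 0.13 | 7.3% to 8.6% |
| 75% × 100% | 0.38 | 0.15 to 0.19 | 10.3% to 13.4% |
| 100% × 100% (ceiling) | 0.50 | 0.20 to 0.25 | 14.5% to 20.1% |

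Worked line, mid-range with SD 2.0: b = 0.5 × 0.50 × 0.75 = 0.1875 h; z = 0.1875 / 0.447 = 0.42; rejection = 6.2% in favour of AIR + 0.9% in favour of control = 7.0% after rounding. Without the artefact each tail would be 2.5%, so all of the excess favours AIR.

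For one person the effect can be larger relative to the score. A Veteran who never sleeps with PAP but does all the practice scores 0.5 h/day in AIR; the same night-time behaviour scores 0 in the control arm. Both stay in the lowest adherence band.

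**The case against.** A reader might infer that AIR prescribes half an hour of awake use a day to the whole arm. The documents do not support that. Practice is tied to an indication, enters the session table conditionally, and is recommended. The share of Veterans who would receive it is not given, nor how many would still be practising four sessions after it starts.

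A reader might also infer that the plan says every device hour counts. It does not say so. This follows only from the absence of a restriction, and the exploratory bands speak of nightly use, which suggests that night use is what the authors have in mind. Nor do the documents describe how the data system counts hours. But the reference to nightly use comes with no method for separating night from awake use, and it does not appear in the definition that the Hypothesis 1b test uses. The sound claim is that the metric is under-defined and, applied as written, can admit practice time.

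The size is also fairly challenged. The upper figure of about 13% needs three quarters of the AIR arm to practise in full every day of the scored week. At mid-range the test moves from 5% to 6–7%, and at the low end it hardly moves. If control Veterans received desensitization in routine sleep care, on which the documents are silent, the difference would shrink.

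On the other side, low uptake cannot be presumed. All participants have insomnia and PTSD, the intervention text describes PAP discomfort as fairly common with PTSD or anxiety, and Veterans may be recruited because their PAP data show non-adherence.

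Finally, an obvious remedy, counting only hours between diary bedtime and rise time, has its own faults. It drops PAP use during naps, still counts practice done in bed, makes a device endpoint depend on complete diaries, and cannot be applied to verbally reported totals. That objection stands, and the fix below does not use such a window.

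**Conclusion.** The point holds in a limited form. For AIR Veterans assigned desensitization, up to 0.5 h/day of awake home practice at the recommended amount can be scored as adherence at post-treatment, and the plan has no rule or sensitivity analysis to deal with it. The direction is towards AIR. The average size depends on share and compliance, both unknown: about 0.06–0.38 h/day, or 0.03–0.19 SD, over the assumed ranges, with a false-positive rate of about 5–13% and about 6–7% at mid-range.

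A reader might conclude that the trial's main result is biased. It is not: the primary outcome is the WHOQOL-BREF psychological domain, which this does not touch. The 3-month PAP comparison is probably little affected, since no homework is described after session 6. What is at stake is one of several Hypothesis 1b outcomes, together with the exploratory bands and the non-adherent subset. It is worth correcting because the remedy is cheap and the ambiguity would otherwise attach to any PAP gain that the pilot reports.

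**What to change.** 1. In the analysis of PAP adherence, state that hours of use exclude awake desensitization practice.
2. Add one line to the existing sleep diary, in both arms, for the clock time and minutes of any awake PAP practice.
3. Remove those minutes from the device hours, matching them to device time stamps where these exist.
4. Report total device hours alongside, so that the group difference is shown with and without practice time.
5. Use the net hours for the exploratory adherence bands and to define the subset not adherent to PAP.

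The diary is already collected during treatment, at post-treatment and at follow-up, so the cost is some wording, one diary item and modest data handling, with no extra visits. The desensitization procedure is unchanged.

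The downside is that where no time stamps exist, as with verbally reported data, the correction relies on self-reported minutes. Over-reported homework would then be over-subtracted, mainly in AIR, and could reverse the bias. Reporting both versions shows how much the conclusion depends on the correction.

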#### **Exploratory Analyses.**

5.0 will be considered acceptable.

**Evaluation of moderators of treatment outcome:** We will evaluate the data for potential moderators of treatment outcomes. This will facilitate adjustments to the protocol prior to a large-scale RCT.

**Analyses:** We will evaluate interactions between subject characteristics and treatment effects to generate hypotheses for informing future work. This exploratory process is necessary because the sample size in the proposed project is insufficiently powered for multiple formal subgroup analyses. In these exploratory analyses, the focus will be on estimated effect sizes rather than statistical significance. These will be calculated based on interaction terms in the models described under Hypothesis 1a above. The primary

moderators of interest are: AHI, concurrent use of sedative-hypnotic medication, baseline PAP self-efficacy (SEMSA), baseline daytime sleepiness (ESS), and baseline sleep quality (PSQI). We will also examine demographic variables and comorbid medical or psychiatric conditions

**Secondary treatment outcomes:** Veterans receiving the behavioral sleep treatment will demonstrate greater increase in sleep efficiency (sleep diary), greater reduction in daytime sleepiness (ESS), greater reduction in PTSD symptom severity (PCL-5), greater improvement in sleep quality (PSQI), and greater improvement in self-efficacy in using PAP (SEMSA) compared with control at post-treatment and follow-up assessment.

**Analyses:** SEF will be the primary variable of interest derived from sleep diaries. The ESS is administered at pre-treatment, sessions 1-6, and post-treatment. The PCL-5, SEMSA, and PSQI are completed at baseline and post-treatment. Separate linear mixed models as described for primary hypotheses 1a and 1b will be estimated for each measure, with each secondary outcome hypothesis tested by the significance of the group difference in baseline-adjusted marginal mean scores post-treatment. Standardized effect sizes will be calculated as the marginal post-treatment group differences divided by pre-treatment standard deviations.

**Evaluation of global treatment satisfaction:** We will examine CSQ-8 total scores for evidence of treatment satisfaction. We will evaluate the data for group differences in treatment satisfaction.

**Analyses:** Descriptive statistics will be calculated for the total score on the CSQ-8. An average total score in the range of 24-32 will be considered acceptable. We will conduct a t-test to compare CSQ-8 total scores in the two conditions.

**Evaluating association between improved sleep and change in functioning:** We will evaluate the relationship between improvement in insomnia and functioning and PAP adherence and functioning.

**Analyses:** We will estimate subject-specific treatment effects on the ISI and WHOQOL-BREF from the mixed models described above, and calculate the Pearson correlation coefficient to assess the relationship between improvement on these two outcomes. We will add PAP adherence as a predictor to the mixed models for WHOQOL-BREF and ISI to test whether changes in functioning or insomnia differ by level of PAP adherence (less than 1 hour nightly, between 1 and 4 hours, greater than 4 hours.)

**CBT-I outcomes among Veterans with uncontrolled OSA:** We will evaluate group differences in insomnia outcomes among the subset of Veterans who do not adhere to PAP during treatment. This will provide data about the efficacy of CBT-I among those with untreated sleep apnea, which is a gap in the literature.

**Analyses:** We will repeat the analyses described above for the ISI and actigraphy outcome measures (hypothesis 1b), in the sample limited to Veterans who are not adherent to PAP.

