Clinical interview. Trained clinical interviewers will conduct the CAPS-5 interview to establish PTSD diagnosis and SCID-5 interview to establish insomnia diagnosis. This will take place over phone or video. The SCID-5 will also be used to rule out diagnostic exclusion criteria and establish comorbid mental health conditions for data analytic purposes. A brief medication interview will be conducted to obtain information about recent and current medication use. Interviews will be audio-recorded and reviewed by the Stress and Health Research Program's clinical assessment supervisor \*This is solely for research purposes.

Baseline prospective sleep data. Once eligibility is established, the Veteran will be shown how to complete a sleep diary. He or she will then record one week of baseline sleep data. Research staff will email the Veteran a link to enter sleep diary data via Qualtrics. The Veteran's PAP setup appointment (if needed) and treatment schedule will be planned. \*This is for research purposes; however, please note that completing a sleep diary is also part of routine care.

**Actigraphy.** The actigraph is a device worn on the risk to measure time asleep vs. awake. A subset of participants will be asked to wear the actigraph. The information will be used solely for research purposes. It is not part of the treatment.

**Baseline appointment**. The Veteran will complete pre-treatment measures. He or she will be randomized to either AIR or SE. \* Many of the pre-treatment measures are completed as part of routine care, but some are added for research purposes.

**Randomization procedure.** A block-randomization procedure will be used to assign participants to AIR or SE in a 1:1 ratio. Block sizes will be a random permutation of 4 and 6. Statistical consultant [REDACTED] will produce the computer-generated list. Each therapist will have his or her own randomization list. The randomization to treatment is for research purposes.

**Weekly assessment.** At the start of each treatment appointment, the Veteran will complete two self-report questionnaires assessing sleep (ISI and ESS). The Veteran's PAP adherence data and actigraphy data will also be downloaded or requested verbally. A copy of the Veteran's sleep diary will be obtained. At his or her final treatment appointment, the Veteran will be asked to complete a sleep diary to submit at the Post-Treatment

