Analyses for insomnia: The ISI is administered several times over the course of treatment: pre-treatment, sessions 1-6, and post-treatment. A linear mixed model will be estimated for each score with subjects entered as a random effect and treatment group entered as a fixed effect. Pre-treatment score will be entered as a covariate. Time (sessions 1-6 and post-treatment) will be modeled linearly and non-linearly, with the choice of functional form governed by likelihood ratio tests and BIC criteria. The choice of whether to include a random effect for time will be determined by choosing the best fitting model according to the likelihood ratio test. All modeling choices will be made before examining any significance tests. The hypothesis will be tested by the significance of the group difference in baseline-adjusted marginal means (least squares means) at post-treatment derived from the full model. The difference in marginal means at post-treatment will be divided by the pre-treatment standard deviation to calculate the standardized effect size. These analyses will be repeated with the insomnia variables of interest derived from actigraphy

(TST and WASO), with data grouped by week. The primary variable for this analysis will be TST.

**Analyses for PTSD:** The CAPS is administered at pre- and post-treatment. The primary analysis examining the CAPS will be based on the CAPS total score. A linear mixed model will be estimated for CAPS total score with subjects entered as a random effect and treatment group and time point entered as fixed effects. The hypothesis will be tested by the significance of the group by time interaction. The baseline-adjusted group difference at post-treatment will be used to calculate the effect size.

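### The exploratory uncontrolled-OSA comparison selects on PAP non-adherence after randomization, which AIR is meant to change, so it should not be described as data on CBT-I efficacy in untreated apnea

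*Combined protocol and SAP*

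**What the plan says.** The paragraph on CBT-I outcomes in uncontrolled OSA (Exploratory Analyses) plans to examine "group differences in insomnia outcomes among the subset of Veterans who do not adhere to PAP during treatment". It adds: "This will provide data about the efficacy of CBT-I among those with untreated sleep apnea". The method is to repeat the Hypothesis 1b ISI and actigraphy analyses "in the sample limited to Veterans who are not adherent to PAP". For the ISI, that hypothesis is decided by the "significance of the group difference in baseline-adjusted marginal means" at post-treatment (Hypothesis Testing, analyses for insomnia).

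Other parts of the plan bear on this:

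- **Timing.** At the baseline appointment, "He or she will be randomized to either AIR or SE". Of PAP use, a 7-day average of hours, the plan says: "This will be measured starting at session 1 and will continue through post-treatment".
- **AIR's target.** PAP adherence strategies are one of AIR's four components (Intervention Descriptions). Barriers to PAP use are worked on weekly, and desensitization is offered to Veterans who have trouble sleeping with the mask. The SE session table lists no PAP content. Hypothesis 1b predicts better PAP adherence with AIR.
- **Link to outcome.** The Scientific Background states that insomnia is associated with PAP non-adherence.
- **Definition.** No cut-off or time window is given for non-adherence here. The bands "less than 1 hour nightly, between 1 and 4 hours, greater than 4 hours" belong to the preceding analysis of PAP use and functioning.
- **Actigraphy.** "A subset of participants will be asked to wear the actigraph", so that version of the analysis has fewer Veterans still.

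**The concern.** Membership of the subset is decided after randomization by a variable that AIR is built to move. If AIR changes who uses PAP, the Veterans left non-adherent in AIR and those non-adherent in SE are different kinds of patient. A difference in ISI between them then mixes any treatment effect with selection. Equal non-adherence rates in the two arms would not settle the matter, because the same percentage can be made up of different people.

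Two further features weaken the efficacy reading. AIR v SE contrasts psychoeducation, motivational interviewing, PAP work and CBT-I together with sleep education, so CBT-I is not isolated even without selection. And with no cut-off, a 4-hour rule would count Veterans with 1-4 hours a night as untreated when they are partly treated.

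At stake is how one exploratory result is read. The plan names this question as a gap in the literature, so a selected contrast could be cited as efficacy evidence.

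**Working it through.** **What the documents give.** There are 40 Veterans per arm, allocated 1:1. There is no expected non-adherence rate, ISI standard deviation or PAP-ISI correlation, so there is no stated figure to reproduce. Everything below is a scenario, not a bound.

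**Assumed model (SD units).**

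- Baseline ISI: b ~ N(0,1).
- Post-treatment ISI without AIR: y0 = 0.5b + e, with var(e) = 0.75. Observed y = y0 - effect × arm.
- PAP use = -r·y (or -r·y0) + sqrt(1 - r²)·noise + d·arm.
- Non-adherent: PAP use below the 60th percentile of SE, so 40 × 0.60 = 24 in SE.
- Bias: baseline-adjusted AIR-minus-SE difference among non-adherers, minus the same difference in everyone. Positive values run against AIR.

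**Scenario A: AIR raises PAP use evenly.** Total shift 0.6 SD, r = 0.5 in both arms, no true ISI effect.

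1. AIR non-adherent share: Φ(0.253 - 0.6) = Φ(-0.347) = 0.364, and 40 × 0.364 = 14.6.
2. Mean ISI among non-adherers is r·φ(z)/p. SE: 0.5 × 0.386/0.60 = 0.322. AIR: 0.5 × 0.376/0.364 = 0.516.
3. The unadjusted difference is 0.516 - 0.322 = 0.19 SD. Adjustment for baseline removes about a quarter. The simulated adjusted bias is 0.15 SD with standard error 0.27, and 0.15/0.27 = 0.56 standard errors.

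If a true ISI effect of 0.80 SD also raises PAP use, the total shift becomes 0.6 + 0.5 × 0.80 = 1.0 SD. Then Φ(0.253 - 1.0) = 0.228, leaving 9.1 AIR non-adherers, and the bias is about 0.27 SD.

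**Scenario B: AIR weakens the link between poor sleep and non-use.** In SE the non-adherers remain the worse sleepers; in AIR less so, or not at all.

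Simulated results (2,000,000 subjects per scenario for bias; repeated trials of 40 per arm for rejection at a nominal 5%, no true ISI effect):

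| Scenario | r in SE / AIR | PAP shift | Bias (SD) | Rejection |
|---|---|---|---|---|
| Equal link, no shift | 0.4 / 0.4 | 0 | 0.00 | 5% |
| A | 0.5 / 0.5 | 0.6 | +0.15 | 8% |
| B, complete loss of link | 0.4 / 0 | 0 | -0.19 | 12% |
| B, complete loss of link | 0.5 / 0 | 0 | -0.25 | 16% |
| B, link halved | 0.4 / 0.2 | 0 | -0.10 | 7% |
| Link halved plus shift | 0.4 / 0.2 | 0.6 | -0.04 | 5% |
| PAP use unrelated to ISI | 0 / 0 | 0.6 | 0.00 | 5% |

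With the arms' roles reversed in B (0 in SE, 0.4-0.5 in AIR), the bias is 0.19-0.25 SD against AIR.

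**Cross-check with a different model.** Let a latent trait drive both PAP use and ISI, with no true ISI effect and no baseline adjustment. Non-adherence of 60% (SE) v 40% (AIR) gives 0.05-0.16 SD against AIR; 60% v 60% gives 0.00.

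**Precision.** With 24 v 24 the standard error is about 0.25 SD (95% interval ±1.96 × 0.25 = ±0.49). With 24 v 15 it is 0.27 SD (±0.53).

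**The case against.** The strongest defence is that this is one item under an exploratory heading in a pilot. The plan concedes it lacks power for multiple formal subgroup analyses, no decision rule uses the result, and providing data about efficacy is milder than claiming to establish it. That is a fair limit on severity. It does not remove the efficacy sentence. The emphasis on effect sizes over significance is written for the moderator interactions in the Hypothesis 1a models, whereas this paragraph repeats the Hypothesis 1b analyses, whose ISI test is one of significance. Reporting effect sizes alone would not undo the selection either.

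A second objection is that the numbers depend on assumptions. That stands, and it rules out several stronger readings a reader might infer:

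- *That the bias is known to flatter AIR, or known to be conservative.* Both signs are plausible, and the two mechanisms can partly cancel.
- *That a bias near 0.27 SD follows from a modest rise in PAP use.* It needs a total shift of about 1.0 SD; at 0.6 SD it is about 0.15 SD.
- *That false-positive rates of 12-16% are typical.* They require the PAP-insomnia link to vanish entirely in AIR while non-adherence rates stay equal, which sits poorly with Hypothesis 1b. Halving the link gives about 7%, and adding a PAP shift about 5%.
- *That the analysis must be dropped, or that it touches the main result.* The primary analyses keep all randomized Veterans.

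The smaller actigraphy sample is a matter of reporting and precision, not a separate flaw.

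**Conclusion.** The structural point holds with high confidence. This AIR v SE contrast is formed by a post-randomization variable that AIR targets, so it is not a randomized comparison, and it does not isolate CBT-I. It cannot support the efficacy description attached to it.

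Size and direction are open. In most of the assumed scenarios the bias is well below one standard error (0.56 in Scenario A), so imprecision usually dominates; only complete loss of the PAP-insomnia link in one arm brings the two to similar size. There is no bias if AIR does not change who uses PAP, or if PAP use is unrelated to insomnia outcome. The first condition would contradict Hypothesis 1b, and the second sits uneasily with the plan's own background. The change should be made, but it concerns the interpretation of one exploratory analysis.

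**What to change.** In the uncontrolled-OSA paragraph of Exploratory Analyses:

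1. Replace the efficacy sentence with a statement that this is a descriptive, non-randomized comparison of AIR with SE, from which no between-arm causal conclusion will be drawn.
2. Before outcome data are examined, define non-adherence by an hours cut-off and a time window. One option is to apply one of the plan's existing bands to the mean of the 7-day PAP values over the treatment weeks.
3. Report estimates with intervals instead of significance tests, beside the all-randomized Hypothesis 1b ISI estimate. Give the number of non-adherers per arm and their baseline ISI, AHI and SEMSA.

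The cost is a wording change and one descriptive table from data already planned, with no new visits or measures. The plan gives up an efficacy statement and leaves that question to a later trial. The baseline table shows only measured differences and cannot prove that the two groups of non-adherers are alike.
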